##### **Total number of hospitalizations for coronary, cerebral, or peripheral ischemia from the time of randomization through 90 days:**

A negative binomial regression model will be fitted to the count data arising from the number of hospitalizations. The model will include fixed effects for treatment, region, index MI type, index MI management, age (as a continuous variable), diabetes, peripheral artery disease, history of prior MI (excluding index MI) and a term for interaction between index MI type and index MI management. The log link function will be used and the log-transformed duration of follow-up within 90 days will be included in the model in order to account for the variable duration of follow-up across subjects. The mean rate of hospitalization per 90 days will be presented by treatment group. A 1-sided  $P$  value for treatment comparison, the rate

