7.4 Multiple Comparisons and Multiplicity

There are two possible sources of multiplicity in this study: one, the planned interim analysis for efficacy; two, the inclusion of three key secondary endpoints along with the primary endpoint in the formal hypothesis testing framework.

Inflation in type I error due to interim efficacy (ie, early termination for benefit) analysis will be controlled with the use of an alpha-spending function from the Rho family, as described in [Section 4.6](#).

Issues related to multiplicity arising from testing the primary endpoint and key secondary endpoints will be addressed using the serial gatekeeping procedure [[Dmitrienko et al, 2013](#)] to control the overall experiment-wise error rate at a 1-sided 0.025 level. Three families of null hypotheses will be defined with family 1 consisting of the primary endpoint (ie, H_{01}), family 2 consisting of the 2 key secondary endpoints (H_{02} and H_{03}) and family 3 consisting of the third key secondary endpoint. The null hypothesis associated with each of these endpoints is given below:

- H_{01} : Hazard ratio (CSL112: Placebo) for time to first CV death, MI, or stroke (from the time of randomization through 90 days) ≥ 1.0
- H_{02} : Rate ratio (CSL112: placebo) of hospitalizations for coronary, cerebral, or peripheral ischemia during 90 days from the time of randomization is ≥ 1.0
- H_{03} : Hazard ratio (CSL112: Placebo) for time to first occurrence of CV death, MI, or stroke from the time of randomization through 180 days) ≥ 1.0
- H_{04} : Hazard ratio (CSL112: Placebo) for time to first occurrence of CV death, MI, or stroke from the time of randomization through 365 days) ≥ 1.0

If H_{01} is rejected at the interim analysis (ie, 1-sided $p < 0.000083$) or at the final analysis, then the hypothesis tests associated with the second family will be performed using the Hochberg procedure at a 1-sided, 0.025 type I error level. The testing will proceed from the

largest to smallest raw P value (step-up). The largest P value will be compared to a 0.025 significance level and if significant, the remaining null hypothesis will also be rejected; if not, the second P value will be compared to a 1-sided 0.0125 significance level. Testing will proceed to family 3 (H_{04}) at a 1-sided 0.025 level only if both family 2 null hypotheses, H_{02} and H_{03} , are rejected.

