10.2 Analysis of Key Secondary Endpoints

The key secondary endpoints will be analyzed based on the ITT population. The null hypothesis associated with each key secondary endpoint will be tested at the time of final analysis. The analysis will be based on CEC-adjudicated events and an assessment of concordance between the investigator-reported and CEC adjudicated events will be undertaken. Multiplicity adjustments are discussed in [Section 7.4](#).

The three key secondary endpoints and their planned analyses are given below:

10.2.1 Total number of hospitalizations for coronary, cerebral, or peripheral ischemia through 90 days after randomization

A negative binomial regression model will be fitted to the count data arising from the number of hospitalizations. This analysis will consider only those hospitalizations adjudicated by the CEC as meeting endpoint criteria. The model will include fixed effects for treatment, region, index MI type, and index MI management, age (as a continuous variable), diabetes, peripheral artery disease, and history of MI, and a term for interaction between index MI type and index MI management which correspond to the covariates in the primary analysis. The log link function will be used and the log-transformed duration of follow-up (based on the date of last MACE ascertainment) within 90 days will be included in the model to account for the variable duration of follow-up across subjects. However, if the model fails to converge then the offset statement will be excluded. The mean rate of hospitalization per 90 days will

be presented by treatment arm. A 1-sided P value for treatment comparison, the rate ratio (CSL112: placebo) and its 95% CI will be estimated from the model.

A cumulative plot of recurrent hospitalization events will be generated using a non-parametric estimator for the mean cumulative function (MCF). Nelson [[Nelson, 2003](#)] introduced the MCF as a way to summarize the average number of events occurring in a subject by time t , within a population exposed to censoring events such as losses to follow-up and termination of the study. It assumes non-informative censoring and the risk set decreases only when an individual is removed from follow-up. A supportive data listing of hospitalization data will be produced.

The SAS code for fitting a negative binomial regression model to the count data from hospitalizations is given in [Appendix 15.5](#).

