In addition, for descriptive purposes, hospitalizations per thousand subject-years of follow-up will be summarized by treatment group.

The leading analysis of the hospitalizations endpoint described above is focused on the estimation of a rate ratio (CSL112: placebo) to determine whether treatment with CSL112 reduces the mean number of hospitalizations during the 90 day period. This approach accounts for death indirectly by adjusting the mean incidence for the duration of exposure but otherwise ignores death in the analysis. Thus, it provides a pharmacoeconomic assessment of treatment benefit afforded by CSL112.

A sensitivity analysis of the hospitalization data will be performed to explicitly incorporate death into the outcome using the Win Ratio [[Pocock et al, 2012](#)] method. This approach recognizes clinical hierarchies within composite outcomes. With the planned endpoint, death will be weighted more heavily relative to the total number of CV hospitalizations during 90 days from the time of randomization. The Win Ratio (CSL112: Placebo) will be calculated along with associated 95% CI and a 1-sided P value. A complete description of the analytical approach is given in [Appendix 15.1](#).

10.2.2 Time to first occurrence of CV Death, MI, or stroke from the time of randomization through 180 days

The derivation of time to first occurrence of CV Death, MI, or stroke from the time of randomization through 180 days is given below. The analytical details are similar to that described for the primary efficacy endpoint and hence a general description is given here.

	Time to Event (days) [TTE]	Censoring Status [Censor]
First of positively adjudicated CV Death, MI, or stroke during the 180 days following randomization	(date of MACE – randomization date) + 1	0
Last MACE ascertainment on or after 180 days of follow-up without experiencing MACE of interest (administrative censoring)	180	1
Discontinue prior to 180 days without experiencing MACE	(date of last MACE assessment – randomization date) + 1	1
Experience non-CV death prior to day 180	(date of death – randomization date)+1	1

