15.5 SAS Code

PROC FREQ (NEWCOMBE WILSON):

```
PROC FREQ DATA=<xxx>;
  TABLE treatment*<endpoint> / RISKDIFF (CL=(newcombe) column=2) OUT=<yyy>;
RUN;
```

Cox Proportional Hazards Regression Model:

PROC PHREG DATA=<xxx>;

```
CLASS TREATMENT MI_TYPE MI_MANAGEMENT REGION PERIPHERAL_ARTERY_DISEASE DIABETES MI_HISTORY;
MODEL <TIME>*<CENSORING>(1) = TREATMENT MI_TYPE MI_MANAGEMENT REGION AGE PERIPHERAL_ARTERY_DISEASE DIABETES
  MI_HISTORY MI_TYPE*MI_MANAGEMENT;
RUN;
```

Negative Binomial Regression Model using PROC GENMOD:

```
PROC GENMOD DATA=;
  Class TREATMENT MI_TYPE MI_MANAGEMENT REGION PERIPHERAL_ARTERY_DISEASE DIABETES MI_HISTORY;
  Model <endpoint> = TREATMENT MI_TYPE MI_MANAGEMENT REGION AGE PERIPHERAL_ARTERY_DISEASE DIABETES MI_HISTORY
    MI_TYPE*MI_MANAGEMENT/ link=log distbn=nb offset=logt;
  Run;
```

Imputation of Missing Baseline Covariates/Risk Factors:

```
PROC MI data= NIMPUTE=1 OUT=;
  CLASS PERIPHERAL_ARTERY_DISEASE DIABETES MI_HISTORY;
  VAR MI_TYPE MI_MANAGEMENT REGION AGE PERIPHERAL_ARTERY_DISEASE DIABETES MI_HISTORY;
  FCS LOGISTIC(PERIPHERAL_ARTERY_DISEASE DIABETES MI_HISTORY / LINK=GLOGIT);
RUN;
```

Tipping Point Analysis:

```
PROC PHREG DATA= ;
  CLASS MI_TYPE MI_MANAGEMENT REGION PERIPHERAL_ARTERY_DISEASE DIABETES MI_HISTORY;
  MODEL AVAL*NCNSR(1)= AGE MI_TYPE MI_MANAGEMENT REGION AGE PERIPHERAL_ARTERY_DISEASE DIABETES MI_HISTORY
    MI_TYPE*MI_MANAGEMENT;
  BAYES SEED=1234 PIECEWISE=HAZARD (INTERVAL=(10 30 50) PRIOR=GAMMA) NBI=2000 THINNING=50 NMC=2500;
  BY TRT;
RUN;
```

One-sided *P* value will be obtained as follows:

The Wald *P* value from the Cox/negative binomial regression model will be transformed to a 1-sided *P* values follows: if the estimated hazard/risk ratio for treatment effect is less than 1, the resulting *P* value will be set to 0.5*Wald *P* value; otherwise, if the estimated hazard/risk ratio is greater than 1 then the result *P* value will be set to 1-0.5*Wald *P* value.

Signature Page

CSL112_3001 - Statistical Analysis Plan - v4 - 11Jan2024

Signed By	Date (GMT)
PPD [REDACTED]	12-Jan-2024 16:00:01
Approved-Biostatistician Lead Approval	
PPD [REDACTED]	14-Jan-2024 20:07:11
Approved-Clinical Development Physician Approval	

Signature Page 1 of 1

--- Do Not Detach This Signature Page ---

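### SAP 10.2.1 drops the follow-up offset if the hospitalization model does not converge, leaving a ratio of mean counts that is still labelled and tested as a rate ratio

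*SAP*

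**What the plan says.** - **Model.** SAP 10.2.1 uses a negative binomial regression with the primary-analysis covariates and a log link. Log follow-up within 90 days, based on the date of last MACE ascertainment, "will be included in the model to account for the variable duration of follow-up across subjects". The code in SAP 15.5 matches: "MI_TYPE*MI_MANAGEMENT/ link=log distbn=nb offset=logt".
- **Fallback.** The next sentence in SAP 10.2.1 reads: "However, if the model fails to converge then the offset statement will be excluded". No substitute is given. The reported quantities remain a mean rate per 90 days by arm and a rate ratio with its 95% CI and one-sided P value.
- **Protocol.** Section 10.3.2.3.1.1 makes no exception: "The log link function will be used and the log-transformed duration of follow-up within 90 days will be included in the model". SAP Section 5 records no change from the protocol-planned analyses.
- **Death.** On the leading analysis, SAP 10.2.1 says: "This approach accounts for death indirectly by adjusting the mean incidence for the duration of exposure but otherwise ignores death in the analysis".
- **Status.** H02 in SAP 7.4 concerns the "Rate ratio (CSL112: placebo) of hospitalizations for coronary, cerebral, or peripheral ischemia during 90 days from the time of randomization". It sits in family 2 with H03, tested by the "Hochberg procedure at a 1-sided, 0.025 type I error level". H04 is tested only if both are rejected.

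**The concern.** The offset is the only term that turns counts into rates. Without it, a subject who dies or is lost on day 5 contributes the same exposure as one followed for 90 days. The SAP's stated route for handling death disappears, and the estimate no longer matches the hypothesis it is used to test.

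H02 is confirmatory. Its P value also affects the level at which H03 is tested under Hochberg, and whether H04 is tested at all. If the CSL112 arm had less follow-up, the fallback would tilt the comparison towards CSL112. If placebo had less, it would make the test conservative.

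**Working it through.** **No stated figure to reproduce.** The documents give no hospitalization rate, dispersion, power or follow-up loss by arm for this endpoint. The only design inputs are 17,400 subjects (8700 per group) and one-sided 0.025. The sample size agrees with the primary design: 17,400 × (6.40% + 5.12%)/2 = 1002 events, against 1004 stated.

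**Bias without the offset.** Under a constant event rate:

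expected ratio = true rate ratio × (mean follow-up CSL112 / mean follow-up placebo).

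If a proportion d leaves early at uniformly spread times, mean follow-up is 1 − 0.5d of the 90 days. With a true ratio of 1 and assumed d:

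- 6% CSL112, 3% placebo: (1 − 0.03)/(1 − 0.015) = 0.970/0.985 = 0.985.
- 4% CSL112, 2% placebo: 0.980/0.990 = 0.990.
- Equal d in both arms: 1.000.

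**Effect on the test.** Type I error ≈ Φ(−1.96 − ln(factor)/SE), with SE = √[2(1/(n·r) + k/n)] and n = 8700. Assumed: 90-day rate r of 0.03, 0.05 or 0.08, and dispersion k of 0 or 1. For r = 0.05 and k = 1, SE = √[2(1/435 + 1/8700)] = 0.0695. A factor of 0.990 then gives Φ(−1.96 + 0.146) = 0.035.

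| Missing person-time, CSL112 / placebo (assumed) | Factor | One-sided type I error over the assumed r and k |
|---|---|---|
| 1% / 1% or 3% / 3% | 1.000 | 0.025 |
| 2% / 1% | 0.990 | 0.033 to 0.038 |
| 3% / 1% | 0.980 | 0.042 to 0.057 |
| 5% / 1% | 0.960 | 0.067 to 0.117 |
| 1% / 3% | 1.021 | 0.010 to 0.014 |

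The 2% / 1% row is the same case as 4% versus 2% early exit.

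**Simulation check.** 400 runs, r = 0.05, dispersion 1, treatment-only model. With 10% versus 2% early exit and no offset, the null ratio was 0.954 with type I error 0.098. With half the events placed in the first 30 days, it was 0.963 and 0.065. With 10% exit in both arms it was 0.998 to 1.002. Keeping the offset, the ratio stayed within 0.994 to 1.004, and type I error (0.0075 to 0.0375, Monte Carlo SE about 0.008) was compatible with 0.025.

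**Can the offset cause non-convergence?** SAP 9.1 sets the last ascertainment date to the randomization date when no other date exists, and a subject can have an event with only days of follow-up. Simulations used 17,400 subjects, 0.05 events per 90 days, dispersion 1 and 3% early exit (all assumed), with 3 to 20 planted subjects having one event and 1 to 7 days of follow-up. They were run in statsmodels, not SAS, with default starting values:

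- Offset and interaction kept: 0/20 converged.
- Offset dropped: 20/20.
- Offset kept, interaction dropped: 0/20.
- Offset kept, started from the no-offset estimates: 20/20.
- No such subjects planted: 20/20 with and without the offset.

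A separate set of 10 runs on data of this kind failed 10/10 from default starts, with or without the interaction. It converged 10/10 from better starting values, and 10/10 as a Poisson model with offset and robust variance.

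Other causes behave differently (40 runs per scenario). With a zero-event interaction cell, usable fits were 5% with offset and interaction, 7.5% after dropping the offset, and 97.5% after dropping the interaction and keeping the offset. With no overdispersion they were 25% with the offset and 27.5% without.

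**The case against.** Several points on the other side have force.

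- **The fallback can work.** A reader might infer that an offset, having a fixed coefficient, can never cause non-convergence. The simulations do not support that: very short follow-up times made the offset model fail, and removing the offset restored convergence. What stands is that this was a starting-value problem, so the offset did not have to go.
- **Bias is conditional.** A reader might infer bias whenever follow-up varies between subjects. It arises in the ratio only if mean follow-up differs between arms. Balanced loss leaves the ratio about unbiased, although the arm-level mean rate per 90 days is understated. Nor would the result be a ratio of raw counts, since all covariates stay in the model.
- **Harm needs a chain of events.** H01 must be rejected, the model must fail, and follow-up must be shorter on CSL112. At 0.985 to 0.990 the shift is a fraction of a standard error.
- **Other outputs would show a distortion.** The SAP reports missing person-years (9.1), and hospitalizations per thousand subject-years, a mean cumulative function plot and a win ratio (10.2.1). None replaces the formal test, and the win ratio in 15.1 compares hospitalization counts to Day 90 without equalizing follow-up.
- **A count ratio may fit the aim.** SAP 10.2.1 also describes the aim as reducing the mean number of hospitalizations over 90 days, and for subjects who die an unadjusted count is close to that. It does not serve subjects lost to follow-up, whose later admissions are unobserved, and H02 is written as a rate ratio.

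**Conclusion.** The point holds. This is a stated rule, not a missing detail. On non-convergence, the formal test of H02 would rest on a covariate-adjusted ratio of mean counts without exposure, contrary to the protocol model and to the SAP's own statement about death. The size depends entirely on a between-arm difference in mean follow-up, for which the documents give no figures. On the assumed exits the factor is 0.985 to 0.990, with no bias in the ratio under equal loss and a conservative test if placebo loses more. At 90 days the bias is probably small, so this is a correction worth making, not a threat to the trial's main conclusion.

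A reader might also infer that the SAP expressly extends the fallback to the 180- and 365-day count endpoints. SAP 10.4 only says that they are analysed in a similar way to 10.2.1, and their P values are descriptive. The carry-over is a reasonable reading but is not stated.

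**What to change.** Delete the fallback sentence in SAP 10.2.1. Replace it with an ordered list that always keeps offset = log(follow-up), with follow-up counted as at least 1 day so that the log is defined:

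1. Refit with other starting values (for example from the Poisson or no-offset fit) or another optimiser.
2. If an index MI type by management cell has zero events, drop that interaction, in line with SAP 8.1.1 and 10.1.1.
3. Fit a Poisson model with the same covariates, the offset and a robust (sandwich) variance.

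Apply the same order to the exploratory count endpoints in SAP 10.4. List steps 2 and 3 in SAP Section 5 as contingencies, since the protocol does not contain them. The cost is a short replacement text and matching code, with no new data. It should be settled before unblinding.

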10.3 Analysis of Other Secondary Efficacy Endpoints

The list of other Secondary Efficacy Endpoints is shown below. These endpoints are not included in the formal hypothesis-testing framework and as such are not part of the Hochberg procedure described in [Section 7.4](#). The P values are intended to be descriptive. The analysis of the secondary efficacy endpoints will be based on the ITT Analysis Set.

1. The time to first occurrence of each individual component of the composite primary efficacy endpoint
 - Time to occurrence of CV death from the time of randomization through 90 days
 - Time to first occurrence of MI from the time of randomization through 90 days
 - Time to first occurrence of stroke from the time of randomization through 90 days

The planned analysis of the components is not designed to take competing risks into consideration. For example, in the analysis of time to occurrence of MI, CV death will be censored. Computationally, this approach is equivalent to the cause-specific hazard ratio that would be obtained for MI in a competing risks framework.

2. Time to occurrence of CV death, Type 1 MI, or stroke from the time of randomization through days 90, 180, and 365
3. Time to occurrence of all-cause death from the time of randomization through 365 days

In the analysis of time to all-cause death (ACD), censoring will be based on the vital status assessment at Day 365 for subjects not completing the study. If subject is alive at Day 365, then subjects will be censored at the time point of interest (days 90, 180, 365). In the analysis of ACD through the end of study, subjects will be censored at Day 365. If Day 365 vital status is unknown, subjects will be censored at the date of last MACE ascertainment.

The analytical approach for the time-to-event endpoints listed above will be similar to that described for the primary endpoint in [Section 10.1.](#); ie, estimates of the 1-sided Wald P value, the hazard ratio and associated 95% CI s will be obtained from a covariate-adjusted Cox proportional hazards regression model with fixed effects for treatment, region, index MI type, index MI management, age (as a continuous variable), diabetes, peripheral artery disease, history of prior MI (excluding index MI) and a term for interaction between index MI type and index MI management in the model. The P values are intended to be descriptive. The effect over time will be illustrated with the complement of (1 - KM) of Kaplan-Meier estimates. Event count (%) will be presented.

A supportive listing of individual subject data including the time to event in days and the censoring variable will be presented.

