9.1 Disposition of Subjects

The study is designed to conclude at least 365 days after the last subject is randomized.

Study visits are expected to be completed in person at all visits except visits 7 (Day 60) and 10 (Day 270) when visit completion by phone contact with subject is permitted. The investigator reports the type of contact at each visit, whether direct contact with subject (in-person or phone) or indirect based on contact with family member or care taker, or primary physician or medical record review, publicly available sources or other. A visit is considered to be complete if the type of contact is direct (in-person or phone) or with family member or care taker since it allows for full ascertainment of MACE. Otherwise, a visit will be considered to be incomplete.

The date of last MACE ascertainment will be derived for each subject and used in the analysis of time-to-event endpoints and count data. It is defined as the later of the last completed visit date or the date of the last positively adjudicated endpoint regardless of event

type. If a subject is missing both dates then the date of last MACE ascertainment will be set to the randomization date.

Subject disposition during the study will be summarized by treatment group and will include the information listed below:

Subject status:

- Number of subjects screened, number of screen failures, and number randomized
 - Of the number randomized, number of subjects receiving all four infusions, fewer than four infusions (discontinued and skipped dose) and no infusion
- Primary endpoint completion status - In order to be defined as a primary endpoint completer, one of the following conditions has to be met:
 - Ascertainment for MACE endpoint has been obtained through Study Day 90 or later or
 - Death prior to Study Day 90
 - Positively adjudicated primary composite MACE prior to Study Day 90
- Study completion status – In order to be defined as a study completer, one of the following conditions must be met:

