- In cases where only follow-up to ascertain vital status at Visit 11 is agreed to: investigator will report that subject did not complete the study due to "other" reason. The investigator will further record the date subject was confirmed to be alive or dead in a free text field on the study conclusion eCRF page. The study day of confirmed to be alive or dead relative to randomization date will be computed and if greater than 365, vital status will be set to Alive. If date confirmed to be alive is less than 365 then vital status at day 365 will be set to Unknown. If date confirmed to be dead is less than 365 then vital status at day 365 will be set to dead.
- In case of complete withdrawal of consent, the date last known to be alive will be reported on the study conclusion eCRF page. A similar derivation as described in the previous paragraph will be applied to determine vital status at study day 365.
- Fraction of missing person years – the primary assessment of the extent of missing data will be based on the proportion of missing person years during the first 90 study days. For calculation of this proportion, subjects completing 90 days of follow-up or experiencing death prior to 90 days are assigned a score of 1 while subjects not completing 90 days of follow-up are assigned a score corresponding to the fraction of

the 90 day follow-up completed. The proportion of missing person years is defined as $1 - (\text{sum(score)}/n)$ where n is the total number of subjects.

A similar statistic will be presented to summarize the extent of missing person years through study day 365.

Analysis Sets:

- Number of subjects included in each of the analysis sets, described in [Section 6](#), will be summarized as counts and percentages

Sub-populations:

- Subjects in each subpopulation as defined by randomization strata will be summarized. The strata information from the eCRF as well as from the IRT system will be presented separately

Enrolment:

- Number randomized will be summarized by region, country, and site

Subject completion by visit:

- Number (%) of subjects completing each planned study visit will be summarized along with the type of contact. Visit completion is defined as direct contact with study participant (in person visit or phone with subject) or indirect contact with family member/care taker.

The following listings of individual subject data will be provided:

- Reason for screen failure as collected in the eCRF

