9.6 Examination of Regions and Timing of First Infusion

Descriptive summaries of the following timings (hours) will be produced by treatment group and region based on the ITT Analysis Set.

- Onset of index MI symptoms to each milestone shown below will be summarized overall and by index MI type:
 - FMC
 - Angiography
 - Randomization
 - First infusion of investigational product
- FMC to start of angiography and end of angiography contrast administration
- FMC to randomization by angiography status and to first infusion
- End of angiography contrast to randomization and to first infusion
- Randomization to first infusion

In addition to the above summaries, time from angiography to start of first infusion will be presented in categories shown below. These data will also be included in a listing of individual subject data.

- <12 hours
- ≥ 12 hours - <24 hours
- ≥ 24 hours - <48 hours
- ≥ 48 hours - <72 hours
- ≥ 72 hours - <96 hours
- ≥ 96 hours - ≤ 120 hours
- >120 hours

10 Efficacy

This section describes the planned analyses of efficacy endpoints. The ITT Analysis Set will be the primary analysis set for all efficacy variables. See the CEC charter for complete definitions of MACE. The primary (or leading) analysis of each composite endpoint including MI will be performed including all MIs.

MACE ascertainment occurs from the time of randomization through Study Days 90, 180, 365, and end of study. Analysis of data from each time period will only include cardiovascular events occurring during that time period. As per the schedule of assessments, the conclusion of study participation is expected to occur between study day 365 and 379 from the time of randomization. Therefore, the end of study period is defined as the time from randomization through the date of study conclusion (even if the study day of conclusion exceeds 379). The analysis of efficacy endpoints through the end of study will include events beyond day 365 and through study conclusion. Cardiovascular endpoints reported and adjudicated after the study conclusion date will not be considered in any of the planned analyses and will instead be limited to a data listing.

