Both the utility score and the EQ VAS are continuous response variables describing the patient's self-assessment of their health status at baseline and post-treatment. Descriptive statistics including the mean, median, SD, minimum and maximum will be provided at baseline, post-treatment and for the change from baseline. The change from baseline will be compared between treatments employing an analysis of variance model (ANOVA) including terms for treatment, region, type of index MI (STEMI vs NSTEMI), management of index MI (PCI vs. medical management), age (as a continuous variable), diabetes, peripheral artery disease, prior history of MI, and a term for interaction between index MI type and index MI management.

Additional Exploratory Efficacy Endpoints

The following additional exploratory efficacy endpoints will be analyzed based on the ITT population. Endpoints consisting of other time points (90, 180, or 365 days) not explicitly listed in this document will also be analyzed.

1. Time-to-occurrence of all-cause death from the time of randomization through 90, 180 days and end of study

2. Time to occurrence of non-COVID-19 related death from the time of randomization through day 365. All deaths resulting from COVID-19 will be censored in this analysis
3. Time-to-first occurrence of CV death or MI from the time of randomization through 90 days
4. Time to first occurrence of CV death, MI, or stroke from the time of randomization through the end of study
5. Time-to-first occurrence of all-cause death, MI, or stroke from the time of randomization through 90 days
6. Time to occurrence of CV death from the time of randomization through 180 days and end of study
7. Time-to-first occurrence of MI from the time of randomization through 180, 365 days and end of study
8. Time-to-first occurrence of stroke from the time of randomization through 180, 365 days and end of study
9. Time to occurrence of thrombotic (ischemic) strokes with hemorrhagic conversion from the time of randomization through day 365
10. Time to occurrence of hemorrhagic stroke from the time of randomization through day 365
11. Time-to-first occurrence of stroke including sub-arachnoid stroke from the time of randomization through days 90, 180 and 365
12. Medical resource utilization from the time of randomization through 180 and 365 days:
 - a. Number of total hospitalizations
 - b. Length of hospital stay
 - c. Number of cardiac care unit (CCU) or intensive care unit (ICU) days

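### All-cause death: non-completers last confirmed alive before Day 365 are censored at last MACE ascertainment, so known survival time is dropped while deaths over the same interval are kept

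*SAP*

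**What the plan says.** All-cause death through 365 days is an other secondary efficacy endpoint (Protocol 2.2.4.1; SAP 4.2 and 10.3). SAP 10.4 adds an exploratory version: "Time-to-occurrence of all-cause death from the time of randomization through 90, 180 days and end of study".

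SAP 10.3 bases censoring of non-completers on Day 365 vital status. Subjects alive at Day 365 are censored at the time point being analysed. Otherwise: "If Day 365 vital status is unknown, subjects will be censored at the date of last MACE ascertainment".

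SAP 9.1 derives that status for subjects who agree only to a vital-status check, and applies a similar derivation after complete withdrawal of consent:

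- Alive: the study day of confirmation "will be computed and if greater than 365, vital status will be set to Alive".
- Unknown: "If date confirmed to be alive is less than 365 then vital status at day 365 will be set to Unknown".
- Dead: "If date confirmed to be dead is less than 365 then vital status at day 365 will be set to dead".

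For complete withdrawals, "the date last known to be alive will be reported on the study conclusion eCRF page". For vital-status-only subjects the date goes in a free-text field on the same page.

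Last MACE ascertainment is "the later of the last completed visit date or the date of the last positively adjudicated endpoint" (SAP 9.1). A completed visit needs direct contact, or contact with a family member or care taker. The last-alive date is not an input.

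The opening of SAP Section 10 adds a cut-off: "Cardiovascular endpoints reported and adjudicated after the study conclusion date will not be considered in any of the planned analyses".

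**The concern.** Take a non-completer last seen at Day 90. Confirmed alive at Day 366, the subject is censored at Day 365. Confirmed alive at Day 360, the subject is censored at Day 90 and 270 days of known survival are lost. Confirmed dead at Day 360, the subject is classed as dead. The choice of censoring date thus depends on the outcome: deaths found between last ascertainment and the vital-status check count, but survivors checked in the same way leave the risk set earlier.

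The same wording governs the 90- and 180-day death analyses, so a subject known to be alive well past those days can still be censored before them.

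Two smaller points sit beside this. First, a date exactly on Day 365 meets neither the greater-than nor the less-than limit, although SAP Section 10 expects study conclusion between Days 365 and 379. Second, the Section 10 cut-off speaks of cardiovascular endpoints, and SAP 10.3 does not say whether it covers deaths found by a vital-status check.

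At stake is the accuracy of the reported death rates and Kaplan-Meier curves, and of the hazard ratio if the affected share or the gap differs by arm.

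**Working it through.** The plan states no figure that depends on this rule, so there is nothing to reproduce. The size has to come from assumptions.

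**Inputs.** From the documents: 17,400 subjects, 8,700 per arm, and analyses at Days 180 and 365. Assumed: 4% one-year mortality at constant hazard, a share f of 2% or 5% affected, and the day last known alive (A) uniform on Days 90-364, with mean (90 + 364)/2 = 227. Three cases for last MACE ascertainment give the mean gap g:

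- 30 days before A: g = 30.
- Uniform from Day 29 to A: g = (227 − 29)/2 = 99.
- Always Day 29 (upper bound): g = 227 − 29 = 198.

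**Hand formula.** Deaths are the same under both rules and only the denominator changes. Ignoring time lost to death, mean follow-up under last-alive censoring is T = (1 − f) × 365 + f × 227. That is 362.24 days for f = 2% and 358.10 for f = 5%. The SAP rule removes f × g, so the rate ratio is R = T / (T − f × g).

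| Gap | R at 2% | R at 5% | Simulated (2%; 5%) |
|---|---|---|---|
| 30 days | 362.24/361.64 = 1.0017 | 358.10/356.60 = 1.0042 | 1.0017; 1.0042 |
| Uniform | 362.24/360.26 = 1.0055 | 358.10/353.15 = 1.0140 | 1.0054; 1.0139 |
| Day 29 | 362.24/358.28 = 1.0111 | 358.10/348.20 = 1.0284 | 1.0110; 1.0282 |

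The simulation, which allows for time lost to death, agrees closely. Person-years dropped are 28-70, 92-229 and 183-458 in the three cases. Kaplan-Meier risk at Day 365 with 5% affected is 4.02%, 4.06% and 4.11%, against 4.00%. For the Day 180 analysis the simulated inflation is 0.1-0.3%, 0.6-1.4% and 1.5-3.9%.

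**Fixed-day example.** Assume 5% mortality, 5% affected, last ascertainment Day 90 and last alive Day 360. A day-by-day expected Kaplan-Meier calculation gives 5.19% against 5.00%. By the hand formula, T = 0.95 × 365 + 0.05 × 360 = 364.75 and f × g = 0.05 × 270 = 13.5, so R = 364.75/351.25 = 1.038.

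**Hazard ratio.** With equal 5% shares, 2,000 simulated trials of 8,700 per arm gave 1.002-1.003, within simulation error of 1. The standard error of log HR is about 2/√(17,400 × 0.04) = 2/√696 = 0.076. With no true effect and shares of 5% versus 2% in the fixed-day example, the hazard ratio is about 1.02.

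**When deaths surface later than last-alive dates.** If deaths are found up to Day 365 but last-alive dates stop earlier, last-alive censoring alone still overstates the true rate by 0.7% (2% affected) or 1.9% (5%). The SAP rule overstates it by 0.9-1.8% or 2.3-4.7%. Stopping both deaths and survival time at last MACE ascertainment gives a ratio of 1.000 in every scenario.

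**The case against.** The affected group may be narrow. Vital-status-only subjects are to be checked at Visit 11, nominally Day 365, so most should be classed Alive. Subjects followed only by record review are derived as Alive. That leaves mainly complete withdrawals, for whom further follow-up is barred unless local regulations allow it. Their last-alive date will often lie close to the last completed visit, which makes the 30-day case the most realistic and the Day 29 case an extreme. With 2% affected, even the extreme ratio of 1.011 gives 4.04%, which prints as 4.0% under the SAP's one-decimal convention. The endpoint is outside the testing hierarchy. The SAP also summarizes Day 365 vital status and missing person-years and lists each subject's censoring variable, so an imbalance would be visible.

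These points bound the size and are accepted. They do not remove the rule, which is stated and treats survivors and deaths differently.

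Two further points have force. SAP 10.3 has no derivation table for all-cause death, so counting a dead subject as an event on the date of death is inferred. Relatedly, an adjudicated cardiovascular death moves the ascertainment date, but the SAP does not make clear that a non-cardiovascular death does. The finding does not need that step, because the death itself is kept either way. Also, last-alive censoring is fully unbiased only if deaths and last-alive dates run to the same cut-off. Protocol 4.3.5 has registries searched until end of study, so this may not hold automatically. That is why the fix includes a common cut-off and a sensitivity analysis.

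**Conclusion.** The concern holds. The SAP discards known survival time for non-completers last confirmed alive before Day 365 while keeping deaths confirmed before Day 365, although the date needed to avoid this is already collected. The bias in absolute mortality is upward and small: 0.2-0.4% relative at Day 365 for a 30-day gap, 0.5-1.4% for a uniform gap, and 1.1-2.8% at the upper bound. These figures rest on the assumed mortality, affected share and gaps. There is no loss when the last-alive date equals last MACE ascertainment. The hazard ratio is essentially unaffected unless the share or the gap differs by arm, and the documents do not suggest that it does. No confirmatory error rate is involved. This should be corrected as a modest matter. The Day 365 limit and the cut-off for late-found deaths are clarifications to settle at the same time.

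**What to change.** In SAP 10.3, for every all-cause-death analysis, censor subjects without a recorded death at the earlier of (a) the analysis time point and (b) the later of last MACE ascertainment and the date last known alive.

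In SAP 9.1, make the limits inclusive: alive if confirmed on or after Day 365, dead if the death is on or before Day 365.

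State that deaths and last-alive dates are taken from the same sources up to the same cut-off, and reconcile this with the study-conclusion rule at the opening of SAP Section 10.

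Add one sensitivity analysis that stops counting both deaths and survival time at last MACE ascertainment.

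The cost is SAP wording, one derivation and one extra run. The dates are already on the study conclusion eCRF page. For vital-status-only subjects the entry is free text, but SAP 9.1 already requires a study day to be computed from it.
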